Statistical Analysis Plan

Dermavant Sciences, Inc. DMVT-505-3101

A Phase 3 Efficacy and Safety Study of Tapinarof for the Treatment of Moderate to Severe Atopic Dermatitis in Children and Adults

Protocol Version/Date: 4.0 09AUG2022

Sponsor: Dermavant Sciences, Inc.

[name]

[name]

Prepared by:

Version	Date
1.0	10AUG2022
2.0	17FEB2023

Revision History

Date	Reason for Update	Section Updated	
10AUG2022	Original Version 1.0	NA	
03FEB2023	Amendment Version 2.0	1. 8. Analysis Sets Added the following categories under • Systemic Agents: Oral/systemic corticosteroids for >5 days; removed "before 8 week visit" Oral PDE4 inhibitors used for atopic dermatitis (e.g., roflumilast, apremilast), or other conditions if not on stable dose for period prior to and over course of the study Oral/systemic retinoids (e.g., alitretinoin), if not on a stable dose for period prior to and over course of the study Other injected monoclonal antibodies with potential impact on AD (omalizumab) Oral/systemic antihistamines for ≥3 days when used for skin conditions Oral/systemic antibacterials for ≥3 days when used for skin conditions Other investigational drug • Topical Agents: Topical antihistamines for ≥3 days when used for skin conditions Other investigational drug 2. 10.4 Handling of Dropouts or Missing Data • Added a note to clarify example SAS code for multiple imputation. • Added a sentence to clarify that unscheduled visits will be included in the LOCF analysis.	

Date	Reason for Update	Section Updated
		Added a sentence to clarify handling more than one PP_NRS records collected on the same day.
		3. 11.1 Primary Efficacy Analyses
		Tipping point analysis:
		 Added a sentence that alternative approaches will be utilized if computational issues are encountered due to a large number of combinations.
		4. 11.2 Secondary Efficacy Analyses
		 Added a sentence that for PP-NRS, if any day of the 7-day period used to compute the average weekly PP-NRS score is on or after the date of the intercurrent event, then the response will be considered a failure for the estimand analysis starting at that visit.
		5. 13.1 Extent of Exposure
		Clarified language around calculation of
		o Number of doses administered
		o Percent compliance
		Removed:
		 A subject will be compliant with the dosing regimen if they applied ≥80% of the expected doses. Expected number of doses is based on length of time enrolled in the treatment-phase of the study.
		6. 13.4 Clinical Laboratory Evaluation
		Added "by visit" for Changes from baseline in abnormality status

LTS	Local Tolerability Scale	
MedDRA	Medical Dictionary for Regulatory Activities	
MI	Multiple Imputations	
NRS	Numeric Rating Scale	
OC	observed cases	
OL-LTE	Open-Label, Long-Term Extension study	
PK	Pharmacokinetic(s)	
PP	Per-Protocol	
PP-NRS	peak pruritus-numeric rating scale (daily itch score)	

Term	Description	
PT	preferred term	
QC	quality control	
QD	once daily	
RTF	rich text format	
SAE	serious adverse event	
SAP	Statistical Analysis Plan	
SAS®	Statistical Analysis Software	
SBP	systolic blood pressure	
SD	standard deviation	
SOC	system organ class	
TEAE	treatment-emergent adverse event	
TF	Treatment Failure	
TLF	tables, listings, figures	
VAS	visual analog scale	
vIGA-AD TM	validated Investigator Global Assessment for Atopic Dermatitis	
WHO-Drug Global	World Health Organization Global Drug Dictionary	

1. INTRODUCTION

This document outlines the statistical methods to be implemented during the analyses of data collected within the scope of Dermavant Sciences, Inc.'s (Dermavant) Protocol DMVT-505-3101 [A Phase 3 Efficacy and Safety Study of Tapinarof for the Treatment of Moderate to Severe Atopic Dermatitis in Children and Adults]. The purpose of this plan is to provide specific guidelines for the statistical analyses. Any deviations from this plan will be documented in the clinical study report (CSR).

2. STUDY DOCUMENTS

The following study documents are used for the preparation of the Statistical Analysis Plan (SAP):

- Protocol, Version 4.0, 09AUG2022
- Annotated case report form (CRF), Version 4, 01JUN2022
- Data management plan, Version 2, 24JUN2022

3. STUDY OBJECTIVES

3.1 Primary Objective

The primary objective of the study is to evaluate the efficacy of tapinar of cream, 1% once daily (QD) compared with vehicle control in subjects with atopic dermatitis (AD).

3.2 Secondary and Exploratory Objectives

The secondary and exploratory objectives of the study are as follows:

- To further characterize the efficacy of tapinar of cream, 1% QD compared with vehicle control over time
- To evaluate the safety and tolerability of tapinar of cream, 1% QD in subjects with AD
- To describe the effect of tapinar of cream, 1% QD on AD symptom severity and the associated impact on daily activities and attitudes in subjects with AD
- To evaluate plasma concentrations of tapinar of in subjects with AD

4. STUDY DESIGN AND PLAN

This is a double-blind, randomized, vehicle-controlled, Phase 3, multicenter study to evaluate the efficacy and safety of topical tapinarof cream, 1% compared with vehicle cream in children and adult subjects (ages 2 and above) with AD.

Following a 30-day screening period, eligible subjects will be randomized at a 2:1 ratio to receive QD treatment with tapinarof cream, 1% or vehicle cream for 8 weeks. Subjects will return to the clinic at Weeks 1, 2, 4, and 8 for efficacy and safety assessments. Additionally, subjects will be contacted by phone at Weeks 3 and 6 to assess adverse events (AEs) and

concomitant medications, to review study drug administration instructions, and to confirm subject's continued participation in this study.

Study drug will be dispensed and applied during the clinic visits and will be administered at home between clinic visits as instructed by site personnel.

Subjects or their caregivers will be instructed to apply study drug QD to all affected areas, including newly appearing lesions and lesions/areas that improve during the study. Subjects or their caregivers will apply sufficient study drug to cover completely each lesion with a thin layer of study drug and will record the time of study drug application and daily itch score (PP-NRS) in a daily diary provided by the study site. Subjects are allowed, but not required, to treat scalp lesions with study drug; however, efficacy analyses will not include assessment of AD in this area. Subjects and/or caregivers will be advised to maintain the approximate dosing time chosen at the beginning of the study for their full study participation. Nonmedicated emollients that do not contain salicylic acid may be used on nonlesional skin, but the subject (or caregiver) should wait at least 30 minutes after applying study drug before applying nonmedicated emollients; emollients should not be applied to lesional skin during treatment. The same emollient should be used throughout the subject's participation in the study. At the phone contacts at Weeks 3 and 6, subjects or caregivers should be reminded to complete their daily diary and bring it with them to the next clinic visit.

Study drug application instructions will be reviewed at all post-randomization clinic visits and during any planned study phone calls. On clinic visit days, subjects and/or caregivers will be instructed/reminded on how to apply study drug (except during the final treatment/end-of-study visits). During the clinic visits, subjects or their caregivers will apply the daily dose of study drug while on-site under the supervision of site personnel after efficacy and safety assessments have been completed, with the exception of the local tolerability scale (LTS) at some visits (as outlined in the Schedule of Assessments [Protocol Table 1]). The time of the dose application and assessments will depend on the time of the clinic visit. Therefore, the timing of the clinic visit may lead to a change in the subject's chosen dosing time for that day.

At the end of the 8 weeks of assessments in this study, subjects will have the option to enroll in an Open-Label, Long-Term Extension (OL-LTE) study for an additional 48 weeks. Subjects who complete Visit 6/Week 8 but choose not to participate in the OL-LTE study or who fail to qualify for participation in the OL-LTE study will complete a Follow-up Visit (Visit 7/Week 9 visit) approximately 1 week after the end of treatment in this study. Subjects who withdraw from the study before Visit 6/Week 8 will complete an Early Termination Visit as their final visit and are not eligible for the OL-LTE study. The subjects who complete the Early Termination Visit must not complete a Follow-Up Visit.

Study duration for subjects who complete this Phase 3 study and who fail to qualify for participation in the OL-LTE study, or who qualify to participate in the OL-LTE study but elect not to enroll in that study is approximately 13 weeks in total. Study duration for subjects who complete this Phase 3 study and are eligible and decide to participate in the OL-LTE study is approximately 12 weeks in total.

Efficacy assessments will include the validated Investigator Global Assessment for Atopic Dermatitis (vIGA-ADTM) score, percentage of total body surface area (%BSA) affected, Eczema Area and Severity Index (EASI), PP-NRS,

Safety assessments will include

treatment-emergent adverse events (TEAEs), clinical laboratory tests, physical examination, vital signs, and electrocardiograms (ECGs) (in a subset of subjects), and investigator and subject/caregiver local tolerability assessments. PK will be assessed in a subset of subjects at Week 4 and Week 8.

Refer to Protocol Section 6 for descriptions of study procedures and assessments and the Schedule of Assessments (Protocol Table 1) for timing of procedures and assessments. The study schema is presented in Protocol Figure 2.

5. DETERMINATION OF SAMPLE SIZE

It is estimated that the proportion of subjects who will achieve a vIGA-ADTM score of 0 or 1 and at least a 2-grade reduction from Baseline to Week 8 will be 45% for subjects receiving tapinarof compared with 25% for subjects receiving vehicle control, based upon the Phase 2 results. With 400 subjects randomized in a 2:1 ratio (267 subjects receiving tapinarof, and 133 subjects receiving vehicle control), this will provide 97.2% power for statistical significance (2-sided p <0.05). The power is calculated from a Fisher Exact sample size calculation. It is assumed that 15% of the subjects receiving tapinarof will be lost to follow-up by 8 weeks compared with 30% of the subjects receiving vehicle control. These subjects will be included in the primary analysis using the multiple imputation method.

6. GENERAL ANALYSIS CONSIDERATIONS

The statistical analyses will be reported using summary tables, listings, and figures (TLFs). The International Council for Harmonisation (ICH) numbering convention will be used for all TLFs. Unless otherwise noted, all statistical testing will be 2-sided and will be performed at the 0.05 significance level. Tests will be declared statistically significant if the calculated p-value is <0.05.

Continuous variables will be summarized by presenting the number of observations, means, standard deviations, medians, minimums, and maximums.

Categorical variables will be summarized by presenting counts and percentages of subjects in corresponding categories. All possible categories as defined in the case report form (CRF) should be populated, even if they have zero counts. Percentages for missing values are omitted and do not account for the percent calculation of other categories. Percentages are based on the total category count excluding the missing category if not otherwise mentioned. In certain tables (e.g., TEAEs), the total number of subjects is used as denominator. Footnotes will specify the percent basis in those cases.

All summary tables will be presented by treatment. Baseline summaries will also include a total summary column.

Individual subject data obtained from the eCRFs, external vendors, central clinical laboratory, ECG laboratory, pharmacokinetic (PK) data, and any derived data will be presented by subject in data listings.

The analyses described in this plan are considered a priori, in that they have been defined prior to database lock.

Any analyses performed after breaking the blind (after database lock, for unblinded studies) will be considered post hoc and exploratory. Post hoc analyses will be labeled as such on the output and identified in the CSR.

All analyses and tabulations will be performed using Statistical Analysis System[®] (SAS[®]) software Version 9.4 or higher. Tables, listings, and figures will be presented in rich text format (RTF).

The process for SAS program validation and quality control (QC) for programs and outputs is documented in the Synteract working instruction "SAS programming quality control." Study-specific QC requirements can be found in Appendix B: SAS programming QC requirements.

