8. ANALYSIS SETS

The safety population will be used for the safety analyses and will include all randomized subjects who receive at least 1 application of study drug. Treatment assignment will be based on the treatment received.

The following subject populations will be used for efficacy analyses:

- The intent-to-treat (ITT) population will include all randomized subjects. Treatment assignment will be based on the randomized treatment.
- The per-protocol (PP) population will exclude ITT subjects with protocol deviations or other events that may impact the interpretation of the primary efficacy endpoint, regardless of whether the deviation(s) is considered major or minor. Exclusion criteria for the Per-protocol population may include:
 - Failure to meet the enrollment inclusion/exclusion criteria
 - Specified use of prohibited concomitant medication

Systemic Agents:

- Oral/systemic corticosteroids for >5 days
- Oral PDE4 inhibitors used for atopic dermatitis (e.g., roflumilast, apremilast); or other conditions if not on stable dose for period prior to and over course of the study
- Any oral immunosuppressive medication including cyclosporine, Imuran (azathioprine), methotrexate, tacrolimus, any Janus kinase inhibitor
- Injected IL4/13 blocking biologic including lebrikizumab, dupilumab
- Oral/systemic retinoids (e.g., alitretinoin), if not on a stable dose for period prior to and over course of the study
- Other injected monoclonal antibodies with potential impact on AD (omalizumab)
- Oral/systemic antihistamines for ≥ 3 days when used for skin conditions
- Oral/systemic antibacterials for ≥ 3 days when used for skin conditions
- Other investigational drug

Topical Agents:

- Topical immunomodulators on affected skin (other than transient <5
 days focal treatment for AESI) including topical corticosteroids, topical
 calcineurin inhibitors (Elidel, Protopic), topical PDE4 inhibitor
 (crisaborole/Eucrisa), coal car containing products
- Topical emollients containing keratolytics (including salicylic acid, urea) on affected skin (other than transient ≤7 days focal treatment for AESI)
- Topical antihistamines for ≥ 3 days when used for skin conditions
- Topical antibacterials limited to gentamicin and neomycin
- Other investigational drug
- Failure to be compliant with treatment regimen (compliance < 80%)
- Inclusion of scalp in efficacy assessment (see protocol section 5.1.5)

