If relationship to treatment is missing, the event will be conservatively treated as related to study drug.

If severity is missing and the AE is reported as serious and fatal, severity will be imputed as CTCAE=5. If severity is missing and the AE is reported as serious and not fatal, severity will be imputed as CTCAE=4. If severity is missing and the AE is not reported as serious, severity will be imputed as CTCAE=3.

All AEs will be listed by treatment and by subject, detailing the verbatim term given by the investigator, the SOC, PT, onset date and time, end date and time, duration (days), common terminology criteria for adverse events (CTCAE) grade, outcome, relationship to study drug, action taken with study drug, other action taken to treat the event, seriousness, and criteria for seriousness. Serious AEs (SAEs), TEAEs leading to study discontinuation, and TEAEs related to study drug will also be listed separately. The following adverse events of special interest (AESIs) will be identified and listed separately: contact dermatitis, follicular event, and headache.

All AEs will be summarized by treatment as incidence rates of:

• Any AE

TEAEs will be summarized by treatment as incidence rates of:

- Any TEAE
- Any AESIs
- Any treatment-related TEAE
- Any TEAE leading to study drug discontinuation
- Any TEAE leading to study discontinuation
- Any SAE (non-Fatal)

- Any serious TEAE
- Death
- Treatment-related Serious TEAE
- Serious TEAE leading to study drug discontinuation
- Serious TEAE leading to study discontinuation
- TEAE (COVID-19) (i.e., positive COVID-19 diagnosis)

Individual PTs will be summarized by treatment according to the following:

- All TEAEs by SOC and PT in descending order of frequency for Tapinarof Cream 1% (also for treatment-related TEAEs, TEAEs leading to study drug discontinuation, TEAEs leading to study discontinuation and serious TEAEs)
- All TEAEs by SOC, PT, and maximum CTCAE grade
- All TEAEs by SOC, PT, and maximum causality (not related, related) to the study drug

In addition, TEAEs and serious TEAEs will be summarized by SOC (alphabetical order) and PT (descending order) for the following subgroups:

- Age (2-6 yrs, 7-11 yrs, 12-17 years, \geq 18 years)
- Sex
- Race (White, Asian, Black or African American and Other)

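### General TEAEs are summarised only as crude percentages of treated subjects, although the plan expects 15% loss on tapinarof and 30% on vehicle by Week 8; a follow-up-adjusted measure should stand beside them

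*SAP*

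**What the plan says.** - **Denominator.** SAP 6: "In certain tables (e.g., TEAEs), the total number of subjects is used as denominator". The safety population in SAP 8 is "all randomized subjects who receive at least 1 application of study drug".
- **Measure.** SAP 13.2: "TEAEs will be summarized by treatment as incidence rates of" a list of categories. A subject with several events counts once at each level, so each figure is a proportion of subjects. Section 13.2 mentions no person-time for general TEAEs.
- **Expected loss.** SAP 5 (and Protocol 10.2) assumes that "15% of the subjects receiving tapinarof will be lost to follow-up by 8 weeks compared with 30% of the subjects receiving vehicle control". For efficacy, multiple imputation deals with this loss.
- **Follow-up-adjusted analysis.** SAP 13.2 plans a Kaplan-Meier figure of time to first event for each AESI (contact dermatitis, follicular event, headache), censored at study completion or discontinuation.
- **Related summaries.** SAP 13.1 summarises days exposed by treatment. SAP 9.1 summarises days in study, completion and reasons for discontinuation.
- **Inference.** SAP 13 plans no formal comparison of safety data.

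**The concern.** Adverse events are recorded only while a subject is followed. Someone who leaves at Week 2 contributes events up to the last contact and is then counted in the denominator like a subject observed for all 8 weeks. Where one arm is expected to lose twice the share of the other, a side-by-side table of crude percentages mixes a difference in risk with a difference in observation time.

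At stake is how the descriptive safety tables read. With equal true risk, tapinarof could appear to cause slightly more adverse events than vehicle, and both arms could understate the 8-week risk. The point concerns loss during treatment, not the follow-up week after Week 8.

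**Working it through.** **The plan's own figure.** The documents give no adverse-event rate to reproduce. The paragraph that holds the loss assumption also states a power: "this will provide 97.2% power for statistical significance (2-sided p <0.05", for 45% versus 25% response with 267 and 133 subjects. Exact enumeration of the two-sided Fisher test gives 97.6%. The continuity-corrected normal formula at 97.2% power returns exactly 133 vehicle subjects. The stated figure is therefore consistent, and the loss assumption is taken as written.

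**Inputs.** From SAP 5: loss L = 0.15 (tapinarof) and 0.30 (vehicle), and arm sizes 267 and 133, all taken as treated. Assumed, because the documents do not give them: the true 8-week risk p, equal in both arms; a constant hazard; the timing of loss; and loss unrelated to adverse events.

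**Formula.** Let r be the probability that a lost subject has an event before leaving.

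- Crude proportion = (1 − L)·p + L·r
- Relative understatement = L·(1 − r/p)

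If p and r are the same in both arms, the ratio of understatements is 0.30/0.15 = 2 at any risk.

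**Numbers for p = 20%.** The hazard is h = −ln(0.8) = 0.2231 per 8 weeks. For loss uniform over a fraction T of the 8 weeks, r = 1 − (1 − e^(−hT))/(hT).

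- T = 1 (whole period): r = 0.1037. Tapinarof 0.85 × 0.20 + 0.15 × 0.1037 = 0.186. Vehicle 0.70 × 0.20 + 0.30 × 0.1037 = 0.171.
- T = 0.5 (first 4 weeks): r = 0.0538. Tapinarof 0.170 + 0.15 × 0.0538 = 0.178. Vehicle 0.140 + 0.30 × 0.0538 = 0.156.

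| Loss pattern | Tapinarof | Vehicle | Understatement | Apparent ratio |
|---|---|---|---|---|
| Uniform, 8 weeks | 18.6% | 17.1% | 7% and 14% | 1.08 |
| Uniform, first 4 weeks | 17.8% | 15.6% | 11% and 22% | 1.14 |

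At true risks of 5% and 40% the apparent ratios are 1.08 to 1.09 (uniform) and 1.13 to 1.14 (early). Under uniform loss, mean follow-up is 0.85 × 8 + 0.15 × 4 = 7.4 weeks on tapinarof and 0.70 × 8 + 0.30 × 4 = 6.8 weeks on vehicle.

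**What the added measure does.** With a constant hazard, expected first events equal h times expected person-time to first event or loss. Events per person-time therefore returns h = 0.2231 in both arms, and 1 − e^(−0.2231) = 20%. This holds only if loss is non-informative.

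**Where the pattern breaks.**

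- *Early events.* If 80% of the cumulative hazard falls in the first 2 weeks and loss is uniform over Weeks 2 to 8, the understatement at 10% risk is only 1.4% and 2.9%.
- *Timing differs by arm* (risk 10% to 30%). With tapinarof loss at Week 1 and vehicle loss at Week 6, the vehicle-to-tapinarof ratio of understatements is 0.51 to 0.55. With Weeks 4 and 6 it is about 1. With Weeks 6 and 1 it is 7.2 to 7.9.
- *Loss linked to adverse events.* With risk 10% in subjects who stay and 30% of lost subjects having an event before leaving, tapinarof is 0.85 × 0.10 + 0.15 × 0.30 = 13% and vehicle is 0.70 × 0.10 + 0.30 × 0.30 = 16%. Vehicle now has the higher figure.

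**The case against.** - **The denominator holds no time.** A reader might infer that unobserved time is counted in the denominator. It is not. The denominator is a count of subjects, and lost subjects contribute every event up to their last contact. Protocol 7.9 asks those who withdraw to attend an Early Termination Visit with adverse-event recording. This stands: the issue is truncated follow-up counted as complete.
- **The 2:1 result is conditional.** A reader might also infer that vehicle rates will be understated twice as much as tapinarof rates, so that the safety comparison is distorted. The documents do not support that. They give no timing of loss, no hazard and no statement that loss is unrelated to adverse events. Protocol 4.6.1 requires withdrawal for related Grade 3 or 4 events, so some withdrawal follows from adverse events by design, and those events are counted. This stands.
- **The gap is small.** It is 1.5 points with uniform loss and 2.2 points with early loss. The standard error of the difference at 20% risk is √(0.20 × 0.80 × (1/267 + 1/133)) = 4.2 points, so the gap is about a third to a half of one standard error. Its modelled direction is unfavourable to tapinarof, so it would not conceal a relative harm. This limits the importance, but sampling error does not excuse a systematic one that is cheap to show.
- **The plan covers part of it.** The AESIs are censored properly, and the exposure and disposition summaries will reveal unequal follow-up. That allows a rough adjustment, but none of it links follow-up to the general TEAE counts.
- **The table list could not be checked.** The list in SAP Appendix C was not in the text reviewed. The statement that general TEAEs have no follow-up-adjusted measure rests on section 13.2.

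**Conclusion.** The point holds as a modest gap in reporting. General TEAEs are crude incidence proportions under the looser name of rates, the plan itself expects twofold differential loss, and only the AESIs get an analysis that accounts for follow-up.

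With similar loss timing in both arms, equal hazard and loss unrelated to adverse events, the relative understatement is twice as large on vehicle, with apparent ratios of about 1.08 to 1.14 under even or early loss and less for events concentrated in the first days. Outside those assumptions neither size nor direction can be stated in advance. The crude table alone cannot show which case applies.

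The 15% and 30% figures are planning assumptions rather than observed loss. No hypothesis test or primary conclusion is affected.

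**What to change.** In SAP 13.2:

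1. Keep n (%) and call it an incidence proportion.
2. For any TEAE, related TEAEs, serious TEAEs and the table by system organ class and preferred term, add the exposure-adjusted rate: subjects with the event divided by person-time from first dose to first event or last adverse-event contact. Alternatively, for the overall categories, extend the Kaplan-Meier method already planned for AESIs and report cumulative incidence at Day 57.
3. State that the two measures are read together. Neither should be the sole basis for statements comparing the arms.
4. For TEAEs leading to discontinuation, keep the crude percentage as the main summary. There the event itself ends follow-up, so the dropout model above does not carry over directly.

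**Cost.** SAP wording, one extra column or a few extra curves, and some programming, using dates already collected. The added measure assumes non-informative loss, and the rate also assumes a roughly constant hazard, so it does not cure loss driven by adverse events. It should be specified before unblinding, because SAP 6 treats later analyses as post hoc.
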